10.2.5 SAEs (Including Deaths) and Adverse Events Leading to Study Drug Discontinuation

Treatment-emergent SAEs (including deaths) and AEs leading to discontinuation of study drug will be summarized by SOC and PT and in listing format.

A listing of pre-treatment SAEs with onset dates prior to the first dose of study drug will be provided.

10.2.6 Safety Topics of Interest

Safety topics of interest will be summarized according to the search criteria are provided in [Appendix B](#).

The final list will be based on the most updated final version of cedirogant Product Safety Statistical Analysis Plan.

Treatment-emergent Safety Topics of Interest will be summarized by SOC and PT and listing format. Additionally, STI rates per 100 patient years of exposure will be provided for each STI category ([Appendix B](#)) in the AE overview summary.

Listings of safety topics of interest will also be provided.

10.3 Analysis of Laboratory Data

Data collected from central and local laboratories, including additional laboratory testing due to an SAE, will be used in all analyses, except for Baseline where SAE-related laboratory assessments on or before the first dose of study drug will be excluded. The clinical laboratory tests defined in the protocol operations manual (e.g., hematology and clinical chemistry) will be summarized.

The raw laboratory variable values and change from baseline to each applicable post-baseline visit will be summarized by treatment group, with number of subjects, mean, standard deviation, median, minimum, maximum. The 95% CI based on normal approximation will be provided for the mean change from baseline.

Laboratory abnormalities meeting CTC criteria grade 3, 4 and ' ≥ 3 ' will be summarized.

Laboratory abnormalities will be evaluated based on Potentially Clinically Important (PCI) criteria ([Appendix C](#)). For each laboratory PCI criterion, the number and percentage of subjects who have a laboratory value meeting the criteria will be summarized. Listings will be provided to summarize subject-level laboratory data for subjects meeting PCI criteria.

Assessment of Liver Enzyme and Bilirubin Elevations

The frequencies and percentages of subjects with post baseline liver specific function test values in ALT/SGPT, AST/SGOT, alkaline phosphatase, and total bilirubin meeting the following criteria will be summarized:

- ALT $> 3 \times$ ULN, $> 5 \times$ ULN, $> 10 \times$ ULN, $> 20 \times$ ULN
- AST $> 3 \times$ ULN, $> 5 \times$ ULN, $> 10 \times$ ULN, $> 20 \times$ ULN
- TBL $> 1.5 \times$ ULN, $> 2 \times$ ULN
- ALT and/or AST $> 3 \times$ ULN and TBL $> 1.5 \times$ ULN
- ALT and/or AST $> 3 \times$ ULN and TBL $> 2 \times$ ULN
- ALT $> 3 \times$ ULN and TBL $> 1.5 \times$ ULN
- ALT $> 3 \times$ ULN and TBL $> 2 \times$ ULN
- Alkaline phosphatase $> 1.5 \times$ ULN

A listing of possible Hy's Law cases, defined as those who meet all of the following conditions simultaneously, will be provided: ALT $> 3 \times$ ULN or AST $> 3 \times$ ULN that is associated with an increase in total bilirubin $\geq 2 \times$ ULN and alkaline phosphatase $< 2 \times$ ULN.

An Evaluation of Drug Induced Serious Hepatotoxicity (eDISH) plot¹ of the maximum post-baseline ALT value (as a multiple of the ULN) vs. the maximum post-baseline total bilirubin value (as a multiple of the ULN), not necessarily concurrent, will also be created. Reference lines will be included at $3 \times$ ULN for ALT and at $2 \times$ ULN for total bilirubin. A similar eDISH plot will be provided for the maximum post-baseline AST value (as a multiple of the ULN) vs. the maximum post-baseline total bilirubin value (as a multiple of the ULN).

10.4 Analysis of Vital Signs

Vital sign measurements of systolic and diastolic blood pressure will be summarized.

The raw value of each vital sign variable and change from baseline at each time point will be summarized by treatment group with number of subjects, mean, standard deviation, median, minimum and maximum. The 95% CI based on normal approximation will be provided for the mean change from baseline.

Vital sign variables will be evaluated based on potentially clinically important (PCI) criteria ([Appendix C](#)) among the Safety Population. For each vital sign PCI criterion, the number and percentage of subjects who have a vital sign value meeting the criteria will be summarized. Listings will be provided to summarize subject-level vital sign data for subjects meeting PCI criteria.

10.5 Safety Subgroup Analyses

There will be no safety subgroup analyses for this study.

10.6 Other Safety Analyses

There will be no other safety analyses for this study.

11.0 Other Analyses

There will be no other analyses for this study.

12.0 Interim Analyses

There were plans for an interim analysis which was to be conducted after the first 140 subjects had either completed the Week 16 assessments or withdrawn from the study. Due to preclinical findings in the cedirogant 39-week dog toxicity study, Study M18-816 was terminated early and no interim analysis will be conducted.

12.1 Data Monitoring Committee

An internal data monitoring committee (DMC) composed of clinicians and statisticians independent of any cedirogant clinical trials outside their role on the DMC, and with relevant expertise in their field will review unblinded safety data from the ongoing study. The primary responsibility of the DMC will be to protect the safety of the subjects participating in this study.

A separate DMC charter describes the roles and responsibilities of the DMC members, frequency of data reviews, relevant data to be assessed, and general operations.

Since there are no efficacy analyses for early stopping, no alpha adjustment is needed.

13.0 Overall Type-I Error Control

There will be no comparison or statistical testing for this Phase 2 study. Overall type I error control is not applicable.

14.0 Version History

Table 1. SAP Version History Summary

Version	Date	Summary
1.0	18 Jan 2022	Original version
2.0	15 Dec 2022	
1. Section 2.0 Study Objectives and Design, due to early termination of the study, the planned interim analysis will not be conducted. The Final database lock will occur after the last on-going subject completes the follow-up phone call.2. Section 7.1 Demographics and Baseline Characteristics, removed Baseline TSQM-9, as TSQM-9 is not collected at baseline.3. Section 9.0 Efficacy Analyses, due to early termination of the study, there will be no comparison or statistical testing for all efficacy endpoints, only summary statistics will be provided. OC will be the approach to handle missing data for categorical and continuous efficacy endpoints instead of NRI-MI and MMRM, respectively.4. Section 10.2 Adverse Events, total patient years is defined as the sum of individual patient year, which is defined as the minimum of (the last dose date + 30 days, the end of study date) minus the first dose date +1, normalized by 365.25 and rounded to one decimal place.5. Section 10.3 added eDISH Plot of AST and removed shift tables.6. Section 12.0 Interim Analyses, due to early termination of the study, the planned interim analysis will not be conducted.

Appendix A. Protocol Deviations

The number and percentage of subjects who reported at least one of the following protocol deviation categories will be provided.

- Subject entered into the study even though s/he did not satisfy entry criteria.
- Subject developed withdrawal criteria during the study and was not withdrawn.
- Subject received wrong treatment or incorrect dose of study.
- Subject took prohibited concomitant medication.

Appendix B. Definition of Safety Topics of Interest for cedirogant

Safety topics of interest (STI) will be identified using the following search criteria:

Safety Topic of Interest	Basis for Inclusion	Criteria for Identification of Event	Are events adjudicated (yes/no)? If yes, external or internal adjudication?	Special Collection Forms or Safety Studies	Relevant Restrictions [#]
Identified Risks - None					
Important Potential Risks					
Serious infection*	Based on the mechanism of action and data from the biomedical literature, as well as information from nonclinical pharmacology and toxicity studies, ABBV-157 administration is expected to produce effects on white blood cells and cytokines. These immunomodulatory properties may result in an increased risk of infection.	Serious events only from the Infections and Infestations SOC	No	No	Exclusion of subjects with HIV, hepatitis B or hepatitis C viral infection. Exclusion of subjects with active severe acute respiratory syndrome coronavirus 2 (SARS-CoV-2) infection.
Other Safety Topics of Interest					
GI tract altered mobility	In rats, GI effects were present at \geq 100 mg/kg/day in the 4-week GLP study and led to marked body weight loss and dehydration, necessitating euthanasia in two animals due to moribund condition. There was also histopathologic evidence of intestinal tract dilation in rats. In the GLP dog study, ABBV-157 produced emesis and loose to watery stools that were well tolerated throughout the study at doses of 40, 120, and 300 mg/kg/day.	Gastrointestinal nonspecific symptoms and therapeutic procedures SMQ_Narrow	No	No	None
Herpes zoster	Manipulating the inflammation cascade with any immune-modulating biologic may increase the risk of infections. Cases of Herpes Zoster is not included in OI CMQ	Herpes Zoster CMQ	No	Yes	None

Safety Topic of Interest	Basis for Inclusion	Criteria for Identification of Event	Are events adjudicated (yes/no)? If yes, external or internal adjudication?	Special Collection Forms or Safety Studies	Relevant Restrictions [#]
Opportunistic infection excluding tuberculosis and herpes zoster	On the basis of MOA and data from the medical literature, as well as information from nonclinical pharmacology and toxicity studies, Cedirogant administration is expected to produce effects on white blood cells and cytokines. These immunomodulatory properties may result in an increased risk of infection.	Opportunistic Infection Excluding Tuberculosis and Herpes Zoster CMQ	No	No	Exclusion of subjects with infection (bacterial, fungal or viral) requiring systemic treatment within 4 weeks of the Baseline Visit.
Active tuberculosis	On the basis of MOA and data from the medical literature, as well as information from nonclinical pharmacology and toxicity studies, Cedirogant administration is expected to produce effects on white blood cells and cytokines. These immunomodulatory properties may result in an increased risk of infection.	Active Tuberculosis CMQ	No	Yes	Exclusion of subjects with active TB and prophylaxis of subjects with latent TB.
Hepatic Disorders	Though there are no signals, preclinical or clinical, of hepatotoxicity associated with ABBV-157 therapy to date, hepatic events are routinely monitored for any drug in development.	Drug Related Hepatic Disorders – Comprehensive Search SMQ _narrow	No	Yes	Exclusion of subjects with AST \geq 2 x ULN or ALT \geq 2 x ULN or total bilirubin $>$ 1.5 x ULN. Exclusion of subjects with history or evidence of HBV or HCV infection.

Safety Topic of Interest	Basis for Inclusion	Criteria for Identification of Event	Are events adjudicated (yes/no)? If yes, external or internal adjudication?	Special Collection Forms or Safety Studies	Relevant Restrictions [#]
Lymphopenia	Non-clinical Findings: Decreased numbers of lymphocyte in the thymus, Peyer's patch, and lymph nodes, along with decreases in thymus weights, were present in rats and dogs and were related to ABBV-157 administration.	Hematological Toxicity - Lymphopenia (Upadacitinib Product Specific) CMQ	No	No	None.
Anemia	Non-clinical Findings: Minimal to mild decreases in RBC mass were present in dogs and rats and were reversible after 4 weeks of recovery.	Non-Hemolytic and Non-Aplastic Anemias CMQ	No	No	Exclusion of subjects with hemoglobin ≤ 9 g/dl.
MACE	There is an increased risk of cardiovascular disease in the psoriasis patient population.	Other Ischaemic heart disease SMQ_narrow Central nervous system hemorrhages and cerebrovascular conditions SMQ_narrow Myocardial infarction SMQ_narrow Death and Sudden Death - HLT	No	Yes	None

Safety Topic of Interest	Basis for Inclusion	Criteria for Identification of Event	Are events adjudicated (yes/no)? If yes, external or internal adjudication?	Special Collection Forms or Safety Studies	Relevant Restrictions [#]
Ocular events	In a healthy volunteer study of an ROR γ t compound related to ABBV-157, 3 of 9 subjects developed eye related events after multiple doses, including one subject who was seen by eye specialists and required prolonged treatment with steroid eye drops and an oral NSAID (aspirin-like drug).	Conjunctival disorders SMQ_narrow Corneal disorders SMQ Scleral disorders SMQ_narrow	No	Yes	Current phase 2b protocol requires any subject with CTCAE Grade 2 or higher AE ocular event must follow up with an ophthalmologist within 7 days. Grade 2 or higher ocular AEs considered related to study drug administration qualify for withdrawal criteria.
Possible malignancies	Comorbidity with patient population, NMSC most common. Theoretical possibility of decreased immune surveillance against malignancies with alteration of immune pathways.	- Malignant tumours SMQ - narrow	No	No	Exclusion of subjects with a history of any malignancy within the last 5 years or documented active malignancy except for successfully treated non-melanoma skin cancer (NMSC) or localized carcinoma in situ of the cervix.
Non-melanoma skin cancer (NMSC)	Comorbidity with patient population, NMSC most common. Theoretical possibility of decreased immune surveillance against malignancies with alteration of immune pathways.	Skin malignant tumours SMQ Broad excluding preferred terms identified by the Melanoma CMQ	No	No	Exclusion of subjects with a history of untreated non-melanoma skin cancer (NMSC).

Safety Topic of Interest	Basis for Inclusion	Criteria for Identification of Event	Are events adjudicated (yes/no)? If yes, external or internal adjudication?	Special Collection Forms or Safety Studies	Relevant Restrictions [#]
Malignant tumours excluding non-melanoma skin cancer (NMSC)	Comorbidity with patient population. Theoretical possibility of decreased immune surveillance against malignancies with alteration of immune pathways.	Malignant Tumours SMQ Narrow EXCLUDING (Skin malignant tumors SMQ Broad excluding PTs identified by Melanoma CMQ)	No	No	Exclusion of subjects with a history of any malignancy within the last 5 years or documented active malignancy except for successfully treated non-melanoma skin cancer (NMSC) or localized carcinoma in situ of the cervix.

* Important risk.

e.g., protocol exclusion criteria or risk minimization actions limiting data on certain patient populations.

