#### Medical Complaints/Adverse Events and Serious Adverse Events

An AE is defined as any untoward medical occurrence in a subject or clinical investigation subject administered a pharmaceutical product and which does not necessarily have a causal relationship with this treatment. An AE can therefore be any unfavorable and unintended sign (including an abnormal laboratory finding), symptom, or disease temporally associated with the use of a medicinal (investigational) product, whether or not the event is considered causally related to the use of the product.

Such an event can result from use of the drug as stipulated in the protocol or labeling, as well as from "special situations" such as accidental or intentional overdose, medication error, occupational or accidental exposure, off-label use, drug abuse, drug misuse, or drug withdrawal, all which must be reported whether associated with an AE or not. Any worsening of a pre-existing condition or illness including chronic plaque psoriasis is considered an AE. Worsening in severity of a reported AE should be reported as a new AE. Laboratory abnormalities and changes in vital signs are considered to be AEs only if they result in discontinuation from the study, necessitate therapeutic medical intervention, meets protocol-specific criteria (see Section 6.2 regarding toxicity management), and/or if the investigator considers them to be AEs.

The investigators will monitor each subject for clinical and laboratory evidence of AEs on a routine basis throughout the study. All AEs will be followed to a satisfactory conclusion.

An elective surgery/procedure scheduled to occur during a study will not be considered an AE if the surgery/procedure is being performed for a pre-existing condition and/or the surgery/procedure has been pre-planned prior to study entry. However, if the pre-existing condition deteriorates unexpectedly during the study (e.g., surgery performed earlier than planned), then the deterioration of the condition for which the elective surgery/procedure is being done will be considered an AE.

If any of the following Safety Topics of Interest events are reported, then the following supplemental report must be completed.

Event	Supplemental Report

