Appendix C. Potentially Clinically Important Criteria for Safety Endpoints

The criteria for Potentially Clinically Important (PCI) laboratory findings are described in Table C-1 and Table C-2, and the PCI criteria for vital sign findings are described in Table C-3.

Table C-1. Criteria for Potentially Clinically Important Hematology Values

Hematology Variables	Units	Definition of Potentially Clinically Important NCI CTCAE (Version 4.03) Grade 3 or greater
		Very Low
Hemoglobin	g/dL	< 8.0
Platelets count	10 ⁹ /L	< 50.0
WBC count	10 ⁹ /L	< 2.0
Neutrophils	10 ⁹ /L	< 1.0
Lymphocytes	10 ⁹ /L	< 0.5

Note: A post-baseline value must be more extreme than the baseline value to be considered a potentially clinically important finding.

Table C-2. Criteria for Potentially Clinically Important Chemistry Values

Chemistry Variables	Units	Definition of Potentially Clinically Important NCI CTCAE (Version 4.03) Grade 3 or greater	
		Very Low	Very High
TBL	mcmol/L		$> 3.0 \times \text{ULN}$
ALP	U/L		$> 5.0 \times \text{ULN}$
SGOT/AST	U/L		$> 5.0 \times \text{ULN}$
SGPT/ALT	U/L		$> 5.0 \times \text{ULN}$
Albumin	g/L	< 20	
Glucose	mmol/L	< 2.2	> 13.9
Triglycerides	mmol/L		> 5.7
Creatinine	mcmol/L		$> 3.0 \times \text{ULN}$ $(> 3.0 \times \text{BL})$
Sodium	mmol/L	< 130	> 155
Potassium	mmol/L	< 3.0	> 6.0
Calcium	mmol/L	< 1.75	> 3.1
CPK	U/L		$> 5.0 \times \text{ULN}$
Total Cholesterol	mmol/L		> 10.34
GGT			$> 5.0 \times \text{ULN}$

Note: A post-baseline value must be more extreme than the baseline value to be considered a potentially clinically important finding.

Table C-3. Criteria for Potentially Clinically Important Vital Sign Values

Vital Signs Variables	Criterion	Definition of Potentially Clinically Important
Systolic Blood Pressure (mmHg)	Low	Value ≤ 90 mmHg and decrease ≥ 20 mmHg from Baseline
	High	Value ≥ 160 mmHg and increase ≥ 20 mmHg from Baseline
Diastolic Blood Pressure (mmHg)	Low	Value ≤ 50 mmHg and decrease ≥ 10 mmHg from Baseline
	High	Value ≥ 100 mmHg and increase ≥ 10 mmHg from Baseline

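### Lymphopenia and anemia are counted only from reported adverse event terms, and no table counts subjects whose blood counts fall to a level short of Grade 3, so a mild effect could be missed.

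*SAP*

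**What the plan says.** **Case finding.** SAP Appendix B identifies lymphopenia by "Hematological Toxicity - Lymphopenia (Upadacitinib Product Specific) CMQ" and anemia by "Non-Hemolytic and Non-Aplastic Anemias CMQ". Both are searches of coded adverse event terms. Neither has a laboratory limit or a special collection form. SAP 10.2.6 reports the topics by system organ class and preferred term, in listings, and as rates per 100 patient-years. It does not refer to the hematology results.

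**Reason for the topics.** Lymphopenia is listed because of animal tissue findings: "Decreased numbers of lymphocyte in the thymus", in Peyer's patch and in lymph nodes, with lower thymus weights. Anemia is listed because "Minimal to mild decreases in RBC mass were present in dogs and rats".

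**When a laboratory value becomes an adverse event.** Protocol 6.1 says "Laboratory abnormalities and changes in vital signs are considered to be AEs only if they result in discontinuation from the study". It then adds three further routes: a need for treatment, meeting a protocol criterion in Section 6.2, "and/or if the investigator considers them to be AEs". The numerical laboratory criteria in Section 6.2 concern creatine phosphokinase and liver tests only.

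**Laboratory analysis.** SAP 10.3 gives by-visit descriptive statistics for values and changes from baseline, summaries of Grade 3, Grade 4 and Grade 3 or worse, and counts and listings of subjects meeting the Appendix C limits. Appendix C is set at "NCI CTCAE (Version 4.03) Grade 3 or greater": hemoglobin below 8.0 g/dL and lymphocytes below 0.5 x 10^9/L. The version history records "added eDISH Plot of AST and removed shift tables", and the current Section 10.3 contains no shift table. That entry is a disclosed change and not an error; what matters is what the current text leaves out.

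**The concern.** Both topics can be read directly from hematology samples. The Study Activities Table schedules these at Screening, Baseline and six later visits (Weeks 2, 4, 6, 8, 12 and 16), plus premature discontinuation. The headline safety count nevertheless ignores those samples and relies on whether an investigator wrote down an adverse event. The one categorical laboratory summary starts at Grade 3, which may be well above a minimal to mild effect of the kind that put anemia on the list.

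The plan is more thorough for the liver. Appendix B says there is no preclinical or clinical liver signal, yet SAP 10.3 counts ALT and AST above 3 x ULN (the Appendix C limit is 5 x ULN) and total bilirubin above 1.5 and 2 x ULN (the Appendix C limit is 3 x ULN), and adds eDISH plots. The two hematology topics that do have animal findings have no counts short of Grade 3.

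SAP 2.1 makes efficacy purely descriptive after early termination, so the safety description is a main remaining output. A topic rate near zero in every arm could be read as absence of a hematology effect when it shows only that few events were reported.

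**Working it through.** The plan states no figure on this point, so there is nothing to reproduce. The check sets the sections side by side and then illustrates the possible size.

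**Step 1. Routes from an asymptomatic fall in hemoglobin or lymphocytes to a topic case**

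| Route in Protocol 6.1 | Open to an asymptomatic, untreated fall? |
|---|---|
| Subject leaves the study because of it | No, if the subject stays |
| Treatment needed | No |
| Meets a Section 6.2 criterion | No; none exists for hematology |
| Investigator considers it an adverse event | Yes, by judgement |

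One route remains. It is open to every abnormality, but its use can vary across about 50 sites.

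**Step 2. What the laboratory section adds**

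| Severity of fall | Subject count by arm | Listing | By-visit mean, SD, median, minimum, maximum |
|---|---|---|---|
| Grade 3 or worse | Yes | Yes | Yes |
| Less than Grade 3 | No | No | Yes |

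The by-visit statistics would show a shift in the mean or an extreme individual value. They do not show how many subjects worsened, or from what starting level.

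**Step 3. Illustration of size.** Let *n* be the arm size, *p* the true laboratory incidence and *s* the share recorded as adverse events. The documents give neither *p* nor *s*, so the values below are assumptions. *n* = 50 is the planned arm size.

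- Expected affected subjects = n x p
- Expected topic cases = n x p x s
- Probability of no topic case = (1 - p x s)^n

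| p | s | Affected | Topic cases | Probability of none |
|---|---|---|---|---|
| 10% | 10% | 5.0 | 0.5 | 0.990^50 = 60% |
| 10% | 25% | 5.0 | 1.25 | 0.975^50 = 28% |
| 10% | 50% | 5.0 | 2.5 | 0.950^50 = 8% |
| 10% | 100% | 5.0 | 5.0 | 0.900^50 = 0.5% |
| 5% | 25% | 2.5 | 0.6 | 0.9875^50 = 53% |
| 20% | 25% | 10.0 | 2.5 | 0.950^50 = 8% |

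At *s* = 100% the topic count equals the laboratory count. The gap is therefore set by reporting practice.

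**Step 4. Arm size.** SAP 2.1 says the study stopped before the planned number was randomized, so the arms are likely to be smaller than 50. With an assumed 30 per arm, *p* = 10% and *s* = 25%, affected subjects are 30 x 0.10 = 3.0, topic cases are 3.0 x 0.25 = 0.75, and the probability of none is 0.975^30 = 47%.

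**The case against.** The strongest reply is that the SAP deliberately keeps two separate streams, coded adverse events and laboratory data, and that the laboratory stream is not empty. Section 10.3 gives means, medians, minima, maxima and confidence intervals for mean change, plus Grade 3 or worse counts and listings. A severe individual fall at a scheduled visit would show in the minimum. This stands. A reader might infer that only visit means could contradict a low topic rate; the documents do not support that.

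A reader might also infer that the topic rates are understated by construction, or that most laboratory abnormalities are excluded. Neither follows. The investigator-judgement clause can admit any abnormality, and Section 6.2 has clinically significant results followed to resolution. Nor do both topics come from animal blood counts: the lymphopenia basis is tissue depletion and thymus weight, and the minimal to mild description belongs to red cell mass alone. An animal severity term also does not translate into a CTCAE grade.

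Adding laboratory values to the topic itself is debatable. SAP 10.2.6 reports topics by preferred term, and a laboratory value has none. Entry allows hemoglobin just above 9 g/dL, so a simple threshold could count trivial changes in subjects who start low. Both are reasons for a separate shift by baseline grade, and neither is a reason for no count.

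Finally, SAP 10.2.6 defers the final topic list to a product-level safety plan that is not available here. That plan could change the search terms, but the SAP as written adds no laboratory link.

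**Conclusion.** The concern holds in a limited form. Lymphopenia and anemia topic rates measure investigator-reported events. They can fall below the laboratory incidence by an amount the documents do not determine. In the illustration this ranges from no gap (everything reported) to 0.5 counted out of 5 affected (one in ten reported). SAP 10.3 covers the severe end properly, but subjects whose counts fall to a level short of Grade 3 are not counted anywhere by arm, and there is no shift table.

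This rests on reading the two queries as searches of adverse event terms, which is how SAP 10.2.6 reports them, and on Section 6.2 having no hematology trigger. The incidence, the reporting shares and the arm size of 30 are assumptions. The effect is on descriptive safety reporting only; no efficacy result, sample size or error rate changes. The change is worth making because the data are already scheduled and the gap covers the mild range that motivated the anemia topic.

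**What to change.** 1. **SAP 10.2.6 and Appendix B:** keep the adverse event counts for lymphopenia and anemia as they are, state that they are investigator-reported events, and cross-refer to the hematology tables in 10.3.
2. **SAP 10.3:** add, by arm and for all active arms combined, a shift from baseline CTCAE grade to worst post-baseline grade for hemoglobin and lymphocytes. An alternative is the number of subjects worsening to each grade, including grades below 3. Show it beside the adverse event counts.
3. **Definitions:** use subjects with a baseline and at least one post-baseline value as the denominator. Name the CTCAE version and give the limits for each grade, since Appendix C lists only Grade 3 limits under version 4.03, while Protocol 6.1 grades adverse event severity under version 5.0.

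The cost is some SAP wording and two or three tables, with no new data collection. The downside is that laboratory-based rates will look higher than the adverse event rates, so the report needs a sentence explaining why they differ.

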10.2.3 Treatment-Emergent Adverse Events by SOC and/or PT

The number and percentage of subjects experiencing TEAEs will be tabulated using the MedDRA system organ class and preferred term, by maximum severity by SOC and PT, and by relationship to the study drug as assessed by the investigator by SOC and PT. Specific adverse events will be counted once for each subject for calculating percentages, unless stated otherwise. In addition, if the same adverse event occurs multiple times within a subject, the highest severity and level of relationship to investigational product will be reported.

In addition, treatment-emergent adverse events will be summarized by PT and sorted by decreasing frequency for the total active group.

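### The Anemia safety topic in SAP Appendix B rests on a query whose name excludes hemolytic and aplastic anemias, and no other row collects them

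*SAP*

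**What the plan says.** SAP Appendix B makes the search the definition of the topic: "Safety topics of interest (STI) will be identified using the following search criteria". The Anemia row lists a single search, "Non-Hemolytic and Non-Aplastic Anemias CMQ". The reason given for including the topic is non-clinical: "Minimal to mild decreases in RBC mass were present in dogs and rats and were reversible after 4 weeks of recovery". Nothing is said about how the red-cell mass fell.

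SAP section 10.2.6 sets the outputs that depend on the search: "Treatment-emergent Safety Topics of Interest will be summarized by SOC and PT and listing format", and "STI rates per 100 patient years of exposure will be provided for each STI category". The rates go into the adverse event overview, which under section 10.2.2 also has a line for any treatment-emergent STI.

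Two further statements bear on the point. Section 10.2.6 says that Appendix B is not the last word: "The final list will be based on the most updated final version of cedirogant Product Safety Statistical Analysis Plan". That plan is not among the documents supplied. And section 10.2.3 covers all treatment-emergent events whether or not they belong to a topic: "The number and percentage of subjects experiencing TEAEs will be tabulated using the MedDRA system organ class and preferred term".

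**The concern.** The label and the search do not match. A reader of the Anemia line will take it to cover anemia. By its name, the query covers anemia less two classes. The basis for the topic does not explain the omission: red-cell mass can fall because cells are destroyed or because too few are made, and the row rules out neither.

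What is at stake is the completeness of one STI category. If a hemolytic or aplastic anemia event occurred, the Anemia summary, its listing and its rate could show nothing for that subject, although the topic was set up to follow a red-cell signal from animals. Since the SAP now has no efficacy testing, safety description is a main product of the study, and its topic tables should cover what their titles say.

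**Working it through.** There is no sample size, power or alpha figure to reproduce. The check is a comparison of texts, followed by an illustration of what one uncounted event is worth.

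**1. Does another row collect the excluded classes?** The Appendix B topics are serious infection, GI tract altered mobility, herpes zoster, opportunistic infection, active tuberculosis, hepatic disorders, lymphopenia, anemia, MACE, ocular events, possible malignancies, NMSC, and malignant tumours other than NMSC. The only other blood-cell topic is lymphopenia. No search is named for hemolytic or aplastic anemia.

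**2. How does Appendix B treat exclusions elsewhere?**
- The row "Opportunistic infection excluding tuberculosis and herpes zoster" states its exclusion in the label, and both excluded conditions have rows of their own. The zoster row even notes that the opportunistic infection query does not cover zoster.
- Malignancy has an overall row, an NMSC row and a row for the remainder.
- Anemia has neither a qualified label nor a companion row.

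**3. Which outputs are affected?**
- Incomplete: the Anemia STI summary by SOC and PT, its listing and its rate (section 10.2.6). The any-STI line (section 10.2.2) is also incomplete unless the subject had another STI.
- Not affected: TEAE tables by SOC and PT, by maximum severity and by relationship (10.2.3); overall exposure-adjusted rates (10.2.4); SAEs and discontinuations, tabulated and listed (10.2.5); hematology values and changes from baseline, CTC grade 3 and 4 summaries, and the PCI summary and listing (10.3), where the hemoglobin criterion in Table C-1 is below 8.0 g/dL.

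The laboratory backstop is partial. A hemoglobin fall that stays at or above 8.0 g/dL gets no categorical flag and shows only in the visit-level summaries.

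**4. What is one uncounted event worth?** Section 10.2.4 counts exposure from the first dose to the earlier of last dose + 30 days and end of study, plus 1 day. For D days of dosing this is (D − 1) + 30 + 1 = D + 30 days. With n subjects, patient-years (PY) = n × (D + 30)/365.25, and one event contributes 100/PY per 100 patient-years. The planned n is 50 per arm (SAP section 2.4), and the planned D is 16 weeks = 112 days.

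| n | D (days) | Exposure (days) | PY | 100/PY |
|---|---|---|---|---|
| 50 (planned arm) | 112 | 142 | 19.44 | 5.14 |
| 150 (planned pooled active) | 112 | 142 | 58.32 | 1.71 |
| 50 | 28 | 58 | 7.94 | 12.59 |
| 25 | 112 | 142 | 9.72 | 10.29 |
| 25 | 28 | 58 | 3.97 | 25.19 |

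The first two rows assume full enrolment and full dosing, which SAP section 2.1 says were not reached. The 25 subjects and 28 days in the other rows are assumptions, because the documents give neither the number randomized nor the exposure. The one-decimal rounding in section 10.2.4 is not applied here; applied to the arm totals it gives 100/19.4 = 5.2 and 100/4.0 = 25.0, so the range of about 5 to 25 stands.

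**The case against.** The case on the other side is substantial.

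- **The term list is not supplied.** The exclusion is inferred from a query name. An event coded to an unspecific anemia term could still be caught. This stands, and the conclusion has to be conditional on the name.
- **The list is not final.** Section 10.2.6 hands the final list to a separate product safety plan. This stands as a limit. But that plan cannot be seen, and its existence does not correct the row as printed.
- **The narrow search fits its basis.** The animal changes were minimal to mild and reversible, and the documents report no hemolytic or aplastic finding. The choice may be deliberate. But the SAP gives no reason, and a mild, reversible fall does not identify a mechanism.
- **The information is reported elsewhere.** This stands and caps the size of the point. The hematology summaries address a fall in red-cell mass more directly than any adverse event query, and they do not depend on coding.
- **Relabelling would be enough.** It would remove the mismatch, but the excluded events would still have no STI row. Appendix B does both things for opportunistic infections.

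A reader might infer that the reported safety data understate anemia risk in the active arms. The documents do not support that: the events remain in the TEAE and SAE tables, the laboratory data are unaffected, and the same query is applied to placebo.

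**Conclusion.** The point holds as a gap in one STI category. If the row is followed as written and the query contains what its name says, a hemolytic or aplastic anemia event in any arm would be absent from the Anemia STI outputs, and possibly from the any-STI line. No test, power figure or safety decision rule in the SAP uses the Anemia rate, and the overall safety reporting is not understated.

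One such event would be worth about 5 per 100 patient-years in a planned arm of 50 with full dosing, and about 5 to 25 under the assumed range of 25 to 50 subjects and 28 to 112 days. These figures might be read as an expected bias. They are not: they give the weight of a single hypothetical event, and the documents give no expected number of events and no actual exposure. Severity is low. This is a cheap improvement.

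**What to change.** In the Anemia row of SAP Appendix B, add the hemolytic and aplastic anemia terms to the search, or add a companion row for them. Make the same change in the product safety plan that section 10.2.6 makes the source of the final list; otherwise it may be lost. Report a total Anemia line with the subset found by the present query shown separately, as the malignancy rows already do. If the narrow search is deliberate, give the reason and state the exclusion in the topic label.

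The cost is SAP wording and a longer term list, with no new data. The downside is a slightly broader total and probably some empty table rows.
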